### **6.6.3. Complete Physical Examinations**

Complete physical examinations, including height (Visit 1 only), skin, nasal cavities, eyes, ears, lymph nodes, genitalia, and respiratory, cardiovascular, gastrointestinal, neurological, and musculoskeletal systems evaluations will be performed as indicated in [Section 5](#).

#### **6.6.4. Limited Physical Examinations**

Limited physical examinations will include evaluations to assess the subject's BD. If a subject presents with symptoms other than BD, the Investigator should determine whether a complete physical examination should be performed.

#### **6.6.5. Vasculitis Assessment**

The PDE4 inhibitors, including apremilast, have been shown to produce inflammatory perivascular histopathological changes in animal studies (eg, rodent toxicology studies). The Investigator should be watchful for any signs and symptoms of vasculitis at all times. Any suspicion of vasculitis must be thoroughly investigated by taking pertinent subject history, doing a physical examination, reviewing AEs, and performing diagnostic procedures as clinically indicated. A subject with signs and symptoms of possible vasculitis should receive a thorough evaluation as described above, managed as medically appropriate, and continued with follow-up until the signs and symptoms of vasculitis have resolved. If vasculitis is assessed as being BD-related, then the vasculitis should be reported on the BD activity pages in the eCRF.

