#### Overview of Safety Assessments

- Adverse events
- Vasculitis and psychiatric evaluations
- Chest radiographs
- Physical examinations
- Vital signs
- Weight measurements
- Clinical laboratory safety evaluations
- Manual 12-lead electrocardiograms (ECGs)
- Pregnancy test

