### **6.6.1. Adverse Events**

The time frames for recording all AEs are indicated in [Section 5](#). It should be noted that during the first 64 weeks of the study worsening of a subject's BD should be considered as worsening of the disease under study, and should not be captured as an AE. Worsening of disease will be captured on a separate BD activity page in the eCRF that lists each of the BD manifestations.

Worsening of a subject's BD will be captured on the AE eCRF for subjects who continue in the optional Open-label Extension Phase after Week 64.

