### **10.9. Other Topics**

## 11. ADVERSE EVENTS

### 11.1. Monitoring, Recording and Reporting of Adverse Events

An adverse event (AE) is any noxious, unintended, or untoward medical occurrence that may appear or worsen in a subject during the course of a study. It may be a new intercurrent illness, a worsening concomitant illness, an injury, or any concomitant impairment of the subject's health, including laboratory test values (as specified by the criteria in [Section 11.3](#)), regardless of etiology. Any worsening (ie, any clinically significant adverse change in the frequency or intensity of a pre-existing condition) should be considered an AE. A diagnosis or syndrome should be recorded on the AE page of the eCRF rather than the individual signs or symptoms of the diagnosis or syndrome.

Worsening of a subject's BD (any manifestation) should be considered as worsening of disease under study, and should not be captured as an AE, unless the event meets the definition of an SAE. Worsening of disease will be reported on the BD activity pages that lists each of the BD manifestations in the eCRF, and not captured in the AE eCRF. See [REDACTED] for more details.

Worsening of a subject's BD will be captured on the AE eCRF for subjects who continue in the optional Open-label Extension Phase after Week 64. Abuse, withdrawal, sensitivity or toxicity to an investigational product should be reported as an AE. Overdose, accidental or intentional, whether or not it is associated with an AE should be reported on the overdose eCRF (see [Section 8.3.2](#) for the definition of overdose). Any sequela of an accidental or intentional overdose of an investigational product should be reported as an AE on the AE eCRF. If the sequela of an overdose is an SAE, then the sequela must be reported on an SAE report form and on the AE eCRF. The overdose resulting in the SAE should be identified as the cause of the event on the SAE report form and in the eCRF but should not be reported as an SAE itself.

In the event of overdose, the subject should be monitored as appropriate and should receive supportive measures as necessary. There is no known specific antidote for apremilast overdose. Actual treatment should depend on the severity of the clinical situation and the judgment and experience of the treating physician.

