## 19. APPENDICES

### Appendix A: List of Behçet's Disease Clinical Features

Behçet Syndrome Diagnostic Criteria
Recurrent oral aphthous ulceration
Skin Lesions
Erythema nodosum
Subcutaneous thrombophlebitis
Papulopustular lesions
Pseudofolliculitis
Acneiform nodules
Positive pathergy test
Cutaneous hypersensitivity
Eye Lesions
Anterior uveitis, Iridocyclitis
Posterior uveitis
Chorioretinitis, retino-vasculitis
Definite history of chorioretinitis or retino-vasculitis
Genital Ulcers
Arthritis without deformity and ankylosis
Gastrointestinal lesions characterized by ileocecal ulcers
Epididymitis
Vascular lesions
Central nervous system symptoms

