11.2. Adverse Events

AEs will be classified using the MedDRA. Unless otherwise specified, AEs will be summarized by system organ class (SOC) and preferred term (PT), with SOCs presented in the standard international order and PTs within each SOC in descending order of subject incidence.

A subject data listing of all AEs (including TEAEs and non-TEAEs) sorted by subject ID and AE start date will be provided based on the safety population, irrespective of analysis periods; this listing will include a “non-treatment-emergent” flag and the date of the last IP dose. Only TEAEs will be included in the AE summaries as described below.

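### Through Week 64, non-serious vasculitis attributed to Behçet's disease is recorded only on the BD activity pages and reaches no safety summary in the visible SAP

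*Protocol*

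**What the plan says.** **Why vasculitis is watched.** Protocol 6.6.5 says that PDE4 inhibitors, apremilast included, "have been shown to produce inflammatory perivascular histopathological changes in animal studies", and asks for vigilance and a full work-up of any suspicion. The Protocol Summary lists "Vasculitis and psychiatric evaluations" among the safety assessments. Table 1 marks the row at each visit, and footnote e qualifies it as an assessment made where appropriate.

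**Where a case is recorded.** Protocol 6.6.5: "If vasculitis is assessed as being BD-related, then the vasculitis should be reported on the BD activity pages in the eCRF". Protocol 6.6.1 says that in the first 64 weeks worsening of BD "should not be captured as an AE. Worsening of disease will be captured on a separate BD activity page in the eCRF". Protocol 11.1 covers worsening of any manifestation and says that it "should not be captured as an AE, unless the event meets the definition of an SAE"; it then describes worsening as reported on the BD activity pages "and not captured in the AE eCRF". In the optional extension after Week 64, worsening of BD goes on the AE page.

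**What is analysed.** SAP 4.2.6.1 defines a TEAE as a kind of AE. SAP 11.2 says: "Only TEAEs will be included in the AE summaries as described below". Protocol 10.7 and SAP 11.2.10 name diarrhea as the only event of special interest.

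**The concern.** Behçet's disease itself affects blood vessels: Protocol Appendix A includes "Vascular lesions" among its clinical features. An attribution to BD is therefore available for a case of vasculitis in either arm. In a single patient, drug and disease are hard to tell apart, and the less subjective evidence is the comparison of randomised groups. The recording rule applies the individual judgement first and removes some cases before that comparison is made. The protocol itself raises this safety question about the drug class, so at stake is whether the study report can answer it with a complete count.

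**Working it through.** The plan has no vasculitis figure to reproduce. Its one design figure, 102 per group, does reproduce (difference 66, SD 144, two-sided 0.05: an exact t-test needs 101.01, rounded up to 102, with power 0.903 at 102). It matters here only as a denominator. The check is mainly a trace of where each kind of case goes.

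| Case | Recorded on | Visible safety output |
|---|---|---|
| Not attributed to BD | AE page | TEAE tables and AE listing |
| Attributed to BD, serious, through Week 64 | AE page, by the exception in Protocol 11.1 | TEAE and serious TEAE tables, SAE listing |
| Attributed to BD, non-serious, through Week 64 | BD activity page only | None found |
| Attributed to BD, optional extension | AE page | Listing only (SAP 11.1) |

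For the third row I looked for any other route into the outputs:

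- SAP 11.1 to 11.4 also summarise laboratory values, vital signs and weight, and SAP 11.2 lists all AEs. None of these shows an event that exists only on a BD activity page.
- Vascular involvement appears inside the BD Current Activity Form and the Behçet's Syndrome Activity Score. The SAP analyses both as efficacy scores, so a vascular item is not reported as an event.
- SAP 8.2 uses the BD manifestation history, but only from the screening and randomization visits.
- Protocol 4.1.1 gives the internal safety team's inputs as AEs, SAEs, discontinuations and laboratory findings. The BD activity pages are not named.

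**Wording of the exception.** Protocol 11.1 keeps serious worsening as an AE. Protocol 6.6.1 and 6.6.5 state the routing without that condition, so a site that follows 6.6.5 alone could file a serious case only on the BD activity page.

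**Illustration on assumed rates.** Let p be the true incidence on apremilast over the period and f the share of cases that are both non-serious and attributed to BD. Neither is in the documents. Among n = 102 subjects, the expected number of vasculitis TEAEs is 102 × p × (1 − f), and the chance of seeing at least one is 1 − (1 − p(1 − f))^102.

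| Assumed p | f = 0 | f = 0.5 | f = 0.75 |
|---|---|---|---|
| 1% | 1.02 expected; 0.64 | 0.51; 0.40 | 0.26; 0.23 |
| 2% | 2.04; 0.87 | 1.02; 0.64 | 0.51; 0.40 |
| 5% | 5.10; 0.995 | 2.55; 0.92 | 1.28; 0.72 |

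Counting both eCRF sources restores the f = 0 column. The table shows only how visibility depends on f; it does not estimate any rate in this trial.

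**The case against.** The strongest reply is that the gap is narrow and perhaps already closed. Several broader readings are tempting, and the documents do not support them.

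- **That every BD-attributed case leaves the safety tables.** A reader of 6.6.5 alone might infer this. Protocol 11.1 retains events that meet the SAE definition, and 11.2.1 counts hospitalization, life-threatening events and important medical events as serious. This stands and limits the point to non-serious events.
- **That SAP Section 11 reports nothing but TEAEs.** The restriction applies to the AE summaries. Laboratory values, vital signs and weight are summarised too, and AEs that are not treatment-emergent are listed.
- **That a full vasculitis evaluation is mandatory at each visit.** Footnote e of Table 1 does not go that far, and Table 2 for the extension has no such row.
- **That the SAP has no analysis of BD manifestations anywhere.** Protocol 11.1 has a redacted cross-reference directly after the text on BD activity pages, and SAP Section 14 cites Sections 4.2.1.3 and 10.2.4, which cannot be seen. An analysis may exist there, so the statement must be confined to the visible SAP.
- **That a pooled table would cleanly separate drug from disease.** Protocol 1.3 reports a greater reduction in overall disease activity on apremilast in Phase 2. If BD vascular disease also fell on apremilast, that benefit could offset a drug-induced excess in the pooled count, so disease events cannot be assumed equal in the two arms. After Week 12 there is no concurrent placebo group.

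It is also fair that exclusion criterion 1 bars active vascular involvement. This should keep events few, and a handful of events supports no formal inference; Protocol 10.7 plans none for safety.

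What remains is that no visible safety output contains the non-serious, BD-attributed cases.

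**Conclusion.** The point holds in a limited form. Through Week 64, non-serious vasculitis that the investigator attributes to BD is recorded only on the BD activity pages and enters no safety summary in the visible SAP. A judgement of cause thus determines which non-serious cases enter the randomised comparison, on a concern that the protocol itself names. The size cannot be derived from the documents, which give neither a vasculitis rate nor the share attributed to BD. It would be wrong to infer that a drug-related excess exists or is likely to be hidden.

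The conclusion assumes that the redacted sections do not already tabulate these events, and that sites apply the exception in Protocol 11.1. It is a cheap improvement to the safety reporting and does not affect the efficacy analysis.

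**What to change.** 1. In SAP 11.2.10, add a summary of all vasculitis and vascular events from the AE and BD activity pages combined, regardless of attributed cause, shown pooled and split by source, with a subject listing. Present it by randomised arm for the placebo-controlled period. For the apremilast-exposure period make it descriptive, with a note that there is no concurrent placebo group.
2. If a redacted section already analyses BD manifestations, cross-refer to it and keep the combined vasculitis summary in the safety section.
3. Reconcile Protocol 6.6.1, 6.6.5 and 11.1 so that the SAE exception reads the same in all three.

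**Cost.** SAP wording, one summary per analysis period and a listing, using existing eCRF pages. The fields of the BD activity page are not shown, and Appendix A names vascular lesions and retino-vasculitis but no general vasculitis item. Confirm first that the events can be identified from that page, and fix the search terms before the 12-week database is unblinded.

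**Downside.** The pooled count mixes disease and drug events, a benefit on BD vascular disease could mask a drug-induced excess, and few events are expected. The split by source helps the reader see this, but the table should be labelled descriptive.

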#### **6.6.6. Psychiatric Evaluation**

During the study (post randomization), any subject who is identified by the Investigator (and/or appropriate site staff) as having a suicide attempt, or major psychiatric illness requiring hospitalization, must be immediately withdrawn from the study and referred for further medical and/or psychiatric care. If a subject is discontinued, the subject should return for the Posttreatment Observational Follow-up Phase Visit.

At any time during the study (post randomization), the Investigator (and/or appropriate site staff) should evaluate any subject who reports thoughts of suicide to determine if the subject truly has suicide ideation. In such a case, the subject will be referred to a psychiatrist for evaluation and treatment as appropriate. The subject may remain on IP until after the psychiatric evaluation, which should be completed within 3 weeks of the referral time. If the psychiatrist deems the subject not to be a risk for suicide, the subject may remain in the study, but if a risk of suicide is confirmed, the subject must be discontinued from the study. If the subject is discontinued, the subject should return for the Posttreatment Observational Follow-up Phase Visit.

A copy of the psychiatric evaluation report must be in the subject's source document, especially if the subject is confirmed not to be at risk for suicide and is continuing in the study.

A Yes/No question should be completed in the eCRF as to whether the subject was sent for a psychiatric evaluation.

#### **6.6.7. Clinical Laboratory Evaluations**

Clinical laboratory evaluations will be performed as indicated in [Section 5](#).

A central laboratory will be used for this study. The Principal Investigator (PI) or medically-qualified designee will review and assess all clinical laboratory results for each subject participating at their sites, and indicate whether the results are clinically significant. The laboratory reports should be initialed and dated by the PI or medically-qualified designee to indicate that they have been reviewed. Abnormal laboratory results may be repeated to rule out laboratory errors. Any clinically significant abnormal laboratory result that is not part of a

clinical diagnosis AE should be reported as a separate AE and should be followed to resolution (ie, stabilizes, returns to baseline, or improves and considered as no longer clinically significant).

Additional clinical safety laboratory evaluations should be performed if judged clinically appropriate by the PI or by a medically-qualified designee, or if the ongoing review of the data suggests a more detailed assessment of clinical laboratory safety evaluations is warranted.

#### **6.6.7.1. Hematology**

As indicated in [Section 5](#), hematology laboratory evaluations will include complete blood count (red blood cell [RBC] count, hemoglobin, hematocrit, white blood cell (WBC) count (absolute and differential), and platelet count.

#### **6.6.7.2. Serum Chemistry**

During Visits 1 and 2, serum chemistry laboratory evaluations will include sodium, potassium, chloride, bicarbonate, calcium, blood urea nitrogen (BUN), creatinine, glucose, albumin, total protein, alkaline phosphatase, bilirubin (total and direct), aspartate aminotransferase/serum glutamic oxaloacetic transaminase (AST/SGOT), and alanine aminotransferase/serum glutamate pyruvic transaminase (ALT/SGPT).

At subsequent visits, as indicated in [Section 5](#), serum chemistry laboratory evaluations will include sodium, potassium, chloride, bicarbonate, BUN, creatinine, glucose, alkaline phosphatase, bilirubin (total and direct), AST/SGOT, and ALT/SGPT.

#### **6.6.7.3. Urinalysis**

Urinalysis will be done at Visit 1 (Screening Visit) and as clinically necessary; dipstick urinalysis (specific gravity, pH, glucose, protein, ketones, bilirubin, and hemoglobin/blood) will be performed. A microscopic urinalysis (epithelial cells, casts, RBCs, and WBCs) will be performed in the event of a positive dipstick result.

#### **6.6.7.4. Hepatitis Testing**

Screening tests for hepatitis B and C antigen or antibodies for study inclusion/exclusion purposes will not be performed. A complete medical history must be taken and must include a query to rule out whether a subject has known active current or history of recurrent infections including hepatitis B and C (see [Exclusion #13](#)). Subjects must be asymptomatic and their liver function test (ie, ALT/SGPT, AST/SGOT, and alkaline phosphatase) levels must be  $\leq 1.5$  x upper limit of normal (ULN) at baseline.

At any time post randomization, a subject's liver function tests should be repeated when ALT/SGPT, AST/SGOT, or alkaline phosphatase levels are  $\geq 2.0$  x ULN. A viral hepatitis panel should be performed together with the repeat liver function tests. A viral hepatitis panel includes total hepatitis A virus antibody (HAV Ab), qualitative hepatitis B surface antibody (HBsAb) and hepatitis B surface antigen (HBsAg) with reflex confirmation, hepatitis B core antibody (HBcAb), and hepatitis C virus antibody (HCV Ab).

### **6.6.8. Contraception Education**

The risks to a fetus or to a nursing child from apremilast are not known at this time. Results of the animal and in vitro studies can be found in the Investigator's Brochure.

Contraception education is for males and females of childbearing potential (FCBP). The Investigator will educate all FCBP and males about the different options of contraceptive methods and their correct use at Visits 1 and 2. All males and FCBP must use one of the approved contraceptive options as described in [Section 7.2](#), while on IP and for at least 28 days after administration of the last dose of the IP.

When a female subject's childbearing potential changes due to a change in contraceptive measures or her ability to become pregnant changes at the time of study entry, or at any time during the study, the Investigator will educate the subject regarding options and the correct and consistent use of effective contraceptive methods in order to successfully prevent pregnancy.

### **6.6.9. Pregnancy Tests for Females of Childbearing Potential**

For all FCBP, pregnancy testing will be performed during the study as indicated in Section 5. A serum pregnancy test with a sensitivity of  $\leq 25$  mIU/mL will be required at Visit 1, Visit 9, after the last dose of IP (eg, the ET Visit), and at the Observational Follow-up Visit, (4 weeks after the last dose of IP). In addition, a local urine pregnancy test kit will be provided by the central laboratory and the test performed on all FCBP subjects at Visit 2 (Baseline Visit; day of randomization) at the site, prior to randomization. A urine pregnancy test(s) should be administered if the FCBP subject misses a menstrual period.

### **6.6.10. Chest Radiograph**

Subjects must have an essentially normal chest radiograph. Results must be within normal limits or not clinically significant in order to allow a subject to enroll in the study.

A chest radiograph (posteroanterior [PA] and lateral views) should be taken prior to Visit 2, when most of the eligibility criteria are met, so that results are available prior to randomization. A PA view is required. An additional lateral view is strongly recommended, but not required. Alternatively, PA or PA/lateral radiographs that were taken within the 12 weeks prior to Visit 1 will be accepted for evaluation for participation in the study.

Additional chest radiographs should be performed as indicated by local treatment guidelines or, if guidelines are not available/applicable, chest radiographs should be performed when clinically indicated.

### **6.6.11. 12-lead ECG**

A 12-lead ECG will be performed during the Screening Phase.

---

 A female of childbearing potential is a sexually mature female who 1) has not undergone a hysterectomy (the surgical removal of the uterus) or bilateral oophorectomy (the surgical removal of both ovaries) or 2) has not been postmenopausal for at least 24 consecutive months (that is, has had menses at any time during the preceding 24 consecutive months).

An ECG will be performed after the subject has been supine for approximately 3 minutes. Sites are to use their own, local ECG machines for the study and the ECG readings will be interpreted by the Investigator by clinically correlating with the subject's condition.

The Investigator's interpretation will be recorded in the ECG eCRF as: normal; abnormal, not clinically significant; or abnormal, clinically significant.

Results must be within normal limits or not clinically significant in order to allow a subject to continue in the study.

## **6.7. Efficacy Assessments**

The following efficacy assessments will be performed as indicated in [Section 5](#).

### **6.7.1. Number of Oral and Genital Ulcers**

The number of oral and genital ulcers will be counted. For females, both vulvar and vaginal ulcers will be counted for genital ulcers.

### **6.7.2. Pain VAS for Oral and Genital Ulcers**

Pain VAS scales (100 mm) for oral and genital ulcers ([Appendix B](#)) will be evaluated separately. These will be completed by the subject on a secure, validated hand-held device. Subjects will be asked to click on a the VAS line at the point that represents the severity of their pain during the previous week, with zero (the left-hand end of the scale) representing no pain and 100 mm (the right-hand end of the scale) representing the worst possible pain.

